Our team has a unique opportunity to leverage and build on existing data and ongoing relationships with a network of motivated ICUs and the Society of Critical Care Medicine. Our team recently partnered with the SCCM to create the "ICU Liberation Collaborative," a QI project to foster the bedside application of the PAD Guidelines through wide-scale dissemination and implementation of the ABCDEF bundle.^{6,27} The Collaborative was led by an internationally recognized, multidisciplinary group with expertise in bundle-related clinical trials, implementation and dissemination research, and large-scale QI efforts. These experts operationally defined the new ABCDEF bundle. The SCCM provided overall project management, and each regional collaborative was led by a team including a registered nurse (RN), medical doctor (MD), respiratory therapist (RT), physical/occupational therapist (PT/OT), and pharmacist to mirror the interprofessionalism implicit in the bundle. The Collaborative included 68 ICUs from academic, community, and Veterans Affairs (VA) hospitals located

throughout the United States. Guided by the Consolidated Framework for Implementation Research (CFIR),⁴⁴ the Collaborative formally ran from August 2015 to April 2017.

Collaborative participants were required to attend four in-person meetings, monthly co-learning calls, and database training sessions. They were also invited to participate in a listserv and select in-person site visits. All teams submitted bundle-related performance and outcome data and completed pre- and post-implementation questionnaires focused on assessment of teamwork, work environment, overall ICU care, and organizational structure (see **APPROACH**).

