Our preliminary data also show that collaborative participation resulted in significant but highly variable ABCDEF bundle adoption. Our next goal was to determine if collaborative participation led to increased bundle adoption. We were interested in exploring if some sites were "better" ABCDEF bundle adopters than others. The presence of a substantial amount of variability in our data would present us the opportunity to learn both from high- and low-bundle-performing sites. We calculated monthly rates of complete bundle performance, proportional bundle performance, and element-specific performance for the 17,258 patients across 49,109 full ICU days. We used segmented regression analysis for interrupted time series data to model the linear trend of bundle performance rates as a function of time for each segment (1-6 months pre-Collaborative involvement and 7-20 months during the Collaborative).

Complete bundle performance levels were low in the baseline (pre-Collaborative) period (i.e., < 4%). Complete bundle performance increased 2.0% (SE = 0.9%, $P = 0.057$) immediately after joining the Collaborative, and each month was associated with 0.6% greater increase (SE = 0.2%, $P = 0.038$) in complete bundle performance rates, compared to a relatively flat trend in the pre-Collaborative period. Proportional bundle performance rates also significantly increased by 3.8% (SE = 1.6%, $P = 0.026$) immediately after joining the Collaborative, then increased monthly at the same speed as the trend in the pre-Collaborative period (2%, SE = 0.4%, $P = 0.57$).

Bundle performance was highly variable among ICUs and across individual bundle elements; interquartile ranges of > 20% existed for all performance measures. (**Figure 1**) Elements A, C, D, and F were performed on average $\geq 70\%$ of the time at the end of the Collaborative:

Figure 1. Variation among ICUs in Unadjusted ABCDEF Bundle Performance Rates

adoption of elements B1, B2, and E (SATs, SBTs, and early mobility) proved far more challenging. For example, at the end of the Collaborative, an average $\leq 40\%$ of patients participated in early mobility and less than half of patients requiring MV received a daily SBT. Although overall performance was relatively poor, there were indeed some very good bundle performers.

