Local staff who attended a training webinar and as-needed support from SCCM managers entered de-identified data into the collaborative database at their individual hospitals. Data were collected retrospectively during a 6-month baseline period (January 2015-June 2015) and prospectively during a 14-month implementation period (January 2016-March 2017). During the baseline (pre-Collaborative) period, staff from each site entered data on the first 5 consecutively admitted ICU patients each month (30 baseline patients per site). Throughout the implementation period, site staff collected data on the first 15 consecutively admitted patients per month. For each patient, daily data were collected for a maximum of seven ICU days (average of 3.3 ICU-days per patient) or until patients transferred out of the ICU, were designated non-ICU status, or died.

Measures. Patient-level variables include: age, sex, race, ethnicity, language, body mass index (BMI), admitting diagnosis, severity of illness, and preadmission residence and mobility status. The severity of illness scores collected in the Collaborative included the Acute Physiology and Chronic Health Evaluation (APACHE) II,¹³⁰ APACHE III,¹³¹ and APACHE IV¹³² referent to the patient's status at the time of ICU admission.

Data analysis. We will conduct similar analyses for each of the performance measures (performed vs. not performed), including complete, proportional, and each element performance. We will first use descriptive statistics to examine data distribution, check for outliers, and summarize patient characteristics. Bivariate tests (e.g., *t* test or Chi-square statistics) will be used to compare patient characteristics in the pre-Collaborative and Collaborative periods.

Using multilevel segmented logistic regression modeling for interrupted time series data, we can model the likelihood of bundle performance change over time, both before and during the periods of Collaborative implementation. **Figure 2** shows a hypothetical example. The basic form of the level-1 model (Figure x, solid black line) can be written as $\text{Logit}(Y_{ij}) = \beta_{0j} +$

Figure 2. Segmented logistic regression for ITS data-A hypothetical example

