β_{1j} Month + β_{2j} Imp + β_{3j} Month * Imp + e_{ij} , where (1) Logit(Y_{ij}) denotes the logit (or log-odds) of receiving bundle performance for the i^{th} ICU-day of the j^{th} patient; (2) Month is the month indicator of the study period (a total of 20 months coded as -5 to 0 for pre-implementation period and 1 to 14 for implementation period); and (3) Imp denotes an indicator variable coded as 0 for pre-implementation period and 1 for the implementation period. Therefore, Logit(Y_{ij}) is modeled as a linear function of $\beta_{0j} + \beta_{1j}$ Month for the pre-implementation period and $(\beta_{0j} + \beta_{2j}) + (\beta_{1j} + \beta_{3j})$ Month for the implementation period. β_{2j} and β_{3j} are the estimates of level and slope changes due to the intervention implementation. A significant level change (β_{2j}) indicates an immediate change in the level of bundle performance at the initiation of intervention implementation. A significant slope change (β_{3j}) indicates different trends over time during the pre- vs. post-implementation periods. Under the multilevel modeling framework, level-2 models will fit β_{0j} , β_{1j} , β_{2j} , and β_{3j} each as a linear function of fixed-effects of patient characteristics and patient-specific random effects. The patient-specific random terms allow for adjustment of within-patient clustering of ICU-days. Take patient gender as an example. From the combined multilevel segmented logistic regression model, we will (1) estimate the overall trends during the pre- and implementation periods (solid black lines); (2) derive fixed-effect estimates by patient characteristics (Figure 4, long dashed line and short dashed line for each gender); (3) test the significance of hypothesized subgroup differences (e.g., older age, obese, and non-English speaking) in the these estimates; and (4) include patient-specific random terms to allow for variability by patients (patient-specific lines not shown in Figure 4). The model can be simplified if supported by the preliminary results. For example, if the initial analyses for an outcome (e.g., element E performance) suggest that (1) there are no significant level change and slope change for both male and female patients and (2) the overall increasing trend over time does not differ by patient gender, we can reduce the model to a parsimonious form using multilevel logistic regression to model the probability of having an outcome as a function of fixed effect of patient gender, fixed effect of time, and patient-specific random effects. We can also further extend the model to (1) include multiple patient characteristics simultaneously in the model to generate multivariable adjusted estimates, (2) perform curve fitting for linear or non-linear trend, and (3) adjust for additional clustering (e.g., within-organization clustering). The above desried multilevel segmented logistic regression approach will be applied to analyzing complete and element bundle performance measures. For proportional bundle performance, we will use multilevel segmented Poisson regression instead.

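### The Aim 1 time axis omits at least six unobserved months, so the level change β2 carries about six times the pre-implementation slope and is not an immediate change at initiation

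*Combined protocol and SAP*

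**What the plan says.** Under Aim 1, Data analysis, the segmented logistic model has terms for Month, Imp and their product, with Month given as "a total of 20 months coded as -5 to 0 for pre-implementation period and 1 to 14 for implementation period". A significant β2, the same section says, "indicates an immediate change in the level of bundle performance at the initiation of intervention implementation". All four coefficients are then modelled "each as a linear function of fixed-effects of patient characteristics and patient-specific random effects".

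The calendar is given elsewhere. Aim 1, Procedures and Data Sources, describes a "6-month baseline period (January 2015-June 2015) and prospectively during a 14-month implementation period (January 2016-March 2017"). Baseline data are sparse: "the first 5 consecutively admitted ICU patients each month (30 baseline patients per site"), against 15 a month later. Preliminary Data states that "the Collaborative formally ran from August 2015 to April 2017".

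The preliminary segmented regression also numbers its months without a break: "1-6 months pre-Collaborative involvement and 7-20 months during the Collaborative". For one measure it reports a jump on joining: "Proportional bundle performance rates also significantly increased by 3.8% (SE = 1.6"%).

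The plan has no gap term, phase-in period or calendar coding. The optional curve fitting for a non-linear trend would run on the same compressed axis.

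**The concern.** In a segmented regression the level change is the vertical distance between two fitted lines at the point where Month × Imp is zero, here Month 0. That distance is an immediate change only if the time axis is true to the calendar at the join. Here about half a year is missing from the axis. Any movement the pre-trend would have produced in that time is counted as level change, as is anything that happened between the August 2015 start and the first implementation observation.

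β2 is one of two change parameters interpreted for every performance measure, and covariates are modelled on it. A covariate placed on all four coefficients (patient characteristics in Aim 1, pre-implementation survey data in Aim 2) passes six times any between-group difference in pre-slope into its effect on the level change.

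**Working it through.** **Month counts.** The codes −5 to 0 and 1 to 14 give 6 + 14 = 20, which reproduces the plan's total. The dates give something else. January to June 2015 is 6 months, and January 2016 to March 2017 is 15 months, not 14. Together that is 21 observed months in a 27-month span, leaving 27 − 21 = 6 unobserved (July to December 2015). If the 14 months are February 2016 to March 2017, the gap is 7.

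**Algebra.** Let T be calendar months with June 2015 = 0, and f the first implementation month (7 for January 2016, 8 for February). Let s be the pre-slope, g the slope change and D the departure from the projected pre-trend at f.

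- Baseline: β0 + sT.
- Implementation: β0 + sT + D + g(T − f).
- The plan's code in the implementation period is Month = T − (f − 1). Substituting gives β0 + s·Month + [D + (f − 1)s − g] + g·Month.

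So coded β2 = D + 6s − g (or D + 7s − g), and coded β3 = g. Fitting the coded model to noise-free data with no true change gives β2/s = 6.0 (January) or 7.0 (February), with β3 = 0. The 6s term is specific to this contrast. If the change is defined at the August 2015 start instead, further multiples of g enter.

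**Size on the odds scale, if the trend continued and nothing else changed.**

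- Monthly odds ratio that alone gives 1.25, the level change in Aim 1, Power analysis: 1.25^(1/6) = 1.038 (1.25^(1/7) = 1.032).
- Element D, stated at up to 0.05 a month in probability. The logit has a slope of at least 4, so this is at least 4 × 0.05 = 0.20 log-odds a month, and exp(6 × 0.20) = 3.3 or more.
- Element E, stated slope zero, and complete performance, described as roughly flat: about no artefact.
- Patient characteristics: reaching the detectable 1.73 needs a between-group pre-slope difference of 1.73^(1/6) = 1.096 a month. The documents give no such differences.

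**Proportional performance, illustration only.** Preliminary Data prints a jump of 3.8 points, then a parenthesis of 2%, SE 0.4%, P = 0.57. If 2% is the monthly pre-trend, the jump against the projected trend is 3.8 − 6 × 2 = −8.2 points. But 2/0.4 = 5, which cannot give P = 0.57. An equal-weight fit to 20 monthly rates, scaled to the printed jump SE of 1.6, gives a pre-slope SE of 0.42 and a slope-change SE of 0.43. Both print as 0.4, so the SE does not say which quantity is meant. P = 0.57 on 16 df needs a t of 0.58, and 0.58 × 0.43 = 0.25, so a slope change of about 0.2% fits equally well. In that case no proportional pre-slope is stated and no corrected figure can be derived.

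**Precision of the alternatives.** This is a weighted fit with 5 patients a month before and 15 after, treating observations as independent. The SE of the level change, in arbitrary units, is:

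| Quantity | SE | Ratio to plan |
|---|---|---|
| Plan's coded β2 | 0.355 | 1 |
| Departure from projected trend, January start | 1.040 | 2.93 |
| Same, February start | 1.145 | 3.22 |
| Fitted June 2015 to first-month change | 0.349 | 0.98 |

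If the ratios carry over, the detectable odds ratio moves from 1.25 to 1.25^2.93 = 1.92 or 1.25^3.22 = 2.05.

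**The case against.** The strongest reply is that little of this reaches the aims. The overall Collaborative effect is not an aim. Under a linear trend β3 is untouched, as are fitted values and the Aim 2 ICU ranking at the last month. Patient-characteristic effects are distorted only if groups differ in pre-slope, and no difference is documented. All of this stands. It limits the consequences without making the stated reading of β2 correct.

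A second reply is that a projection over seven months from six sparse baseline months is too imprecise to be the only level change reported. That also stands, and the fix pairs it with another contrast. The plan's smaller SE, however, belongs to a different quantity: a distance between lines on a compressed axis.

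A reader might infer from −8.2 that proportional performance fell below trend, or that the reported +3.8 is refuted. The documents do not support this, because the figure depends on one reading of an inconsistent parenthesis and on a trend that continued through unobserved months. A reader might also extend the point to the post-implementation organizational survey and the Aim 3 strategies, which are described as entering only level and slope change. Whether those models need a pre-slope term is a separate question. It would arise without any gap, and recoding Month would not settle it.

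**Conclusion.** The point holds. As coded, β2 is the departure from the projected trend at the first implementation month plus 6 (or 7) times the pre-slope minus the slope change. Even with a flat baseline it is not an immediate change at initiation, because the first implementation observation comes about five months after the formal start. The same multiple enters covariate effects on the level change for patient characteristics and pre-implementation survey data, in proportion to any pre-slope difference between groups.

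The algebra follows from the stated codes and dates and is certain. The practical size is not. It is about nil for complete performance and element E. For element D it could reach an odds ratio of 3.3 or more, but only if its trend persisted. It cannot be settled for proportional performance or for subgroups. It would be too strong to say that the plan's level changes are spurious or that its other outputs are invalid.

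**What to change.** 1. Reconcile the 14-month duration with the 15 months from January 2016 to March 2017, and state the first implementation month f.
2. Code Month in calendar months with June 2015 = 0 (f = 7 for January 2016, 8 for February), and replace Month × Imp by (Month − f) × Imp in both the logistic and Poisson models.
3. Remove the word *immediate*. Define β2 as the departure from the projected pre-implementation trend at the first implementation month, about five months after the Collaborative began.
4. Because that projection rests on six sparse months, report beside it the fitted change from June 2015 to the first implementation month. State that this contains 7 (or 8) times the pre-slope if the trend continued.
5. Restate the level-change power for whichever quantity is reported.

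The cost is one recoded variable, one re-centred term, a few lines of text and a rerun of the level-change power simulation. No new data are needed. The price is precision: on the independence approximation the projected level change has about 2.9 to 3.2 times the plan's SE, so the stated detectable odds ratio becomes less favourable, about 1.9 to 2.05. The June-to-first-month change costs essentially nothing in precision.

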
Power analysis. We used the simulated-based power calculation method by Zhang et al.¹³³ for interrupted time series analysis to conduct power analysis for Aim 1. With the expected ~49,000 ICU-days of ~15,000 patients in 68 ICUs, we generated 1,000 simulations with various patient subgroup distributions and proportion of ICU days with bundle performance during the pre-implementation and implementation periods. Our preliminary analyses of the pre-implementation period data suggest that the probability of bundle performance ranged from 0.05 (for complete bundle performance) to 0.60 (for performance of element A) at the end of the pre-implementation period and a monthly increase in the probability ranged from zero (for element E) to 0.05 (for element D). To be conservative in power calculation, we used a probability of 0.05 for the level and a 0.05 monthly increase in the probability for the slope in the pre-implementation period. Our power analysis suggested that our data will have 80% power to detect an odds ratio (OR) of 1.25 (corresponding to an increase of 0.02 in the probability of receiving bundle performance) and 80% power to detect a slope change, with an OR of 1.52 corresponding to pre- vs. post-difference of 0.03 in the monthly increase of the probability of receiving bundle care. Based on our preliminary data, we reasonably assumed an autocorrelation of 0.5 under the first order auto-regressive covariance structure, a within-patient correlation of 0.5, and a within-hospital correlation of 0.6 in our simulation-based power calculation. Under the same assumptions, we also conducted power analyses on the effects of patient characteristics on the level and slope changes. For patient characteristics with 20:80 distribution, our sample size will have 80% power to detect an OR of 1.73 for the effect of patient characteristics on level change and 80% power to detect an OR of 2.65 for the effect of patient characteristic on slope change. The above power calculation is the most conservative scenario. The study power will be greater than 80% for other cases (e.g., pre-probability of 0.5, patient characteristics with 50:50 distribution). Regardless of study power, we will report point estimates, 95% confidence intervals, and use clinical significance to guide results interpretation. All above calculations were based on multilevel segmented logistic regression with a 0.05 two-sided significance level and adjusted for data dependencies described above.

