Sample Size/Power Analysis. The reliability of ICU-specific performance rates depends on sample size in each hospital (ICU days after adjusting for within-patient clustering). Using the Spearman-Brown prophecy formula,^{138,139} a minimal sample size of 10 is needed to generate reliable ICU-specific estimates (reliability ≥ 0.8), assuming an intraclass correlation of 0.3 for between-ICU variation based on our preliminary analysis. Given the large number of observations in our data ($\sim 49,000$ ICU patient-days nested in $\sim 15,000$ patients in 68 ICUs), there will be sufficient sample size to generate an ICU-specific performance estimate with ≥ 0.8 reliability, even conservatively assuming a large within-patient correlation of 0.8. We conducted power analysis for the effects of organization-level characteristics using the same simulation-based approach described for Aim 1 power analysis. Under the most conservative scenario (see power analysis of Aim 1), our sample size will have sufficient power ($\geq 80\%$) to detect an OR of 1.80 for the effect of an implementation strategy (used vs. not used by the site) on level change and an OR of 2.96 for the effect of an implementation strategy in slope change, assuming 20:80 distribution of the implementation strategy (used vs. not used by the site).

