Data Analysis. The overall analytic strategy for Aim 2 will be the same as described for Aim 1. That is, using multilevel segmented logistic regression modeling for complete and element bundle performance and multilevel segmented Poisson regression for proportional performance. First, we will examine the variation across ICUs in bundle performance by adding ICU-specific random effects to the model. All significant patient-level characteristics from Aim 1 will remain in the model as covariates so that ICU-level estimates are risk-adjusted for patient case mix. From the model, we can (1) quantify the degree of ICU variation using the intra-class correlation (ICC); (2) derive the ICU-specific adjusted rates of bundle performance at the last month of implementation and examine their distribution (mean, variance, median, interquartile range, and range); and (3) rank the ICU-specific adjusted rates from low to high and identify the top 5 and bottom 5 ICUs with best and worst adjusted performance rates. Next, we will estimate the effects of organizational characteristic on bundle adoption by adding them as fixed effects to the model. Organizational survey at the post-implementation period will be estimated as fixed effects to model the level change (β_{2j}) and slope change (β_{3j}). While data from the pre-implementation period will be estimated as fixed effects to model pre-implementation level (β_{0j}), pre-implementation slope (β_{1j}), post-implementation level change (β_{2j}), and slope change (β_{3j}) (see **Data Analysis section for Aim 1**). Again, multilevel clustering (within-patient clustering of ICU days and within-ICU clustering of patients) will be adjusted in the model using random effects terms. As the provider-level data can be linked to specific ICUs, but not linkable to specific patient and patient ICU days, we will use multilevel modeling (level-1: time-point [pre- and post-survey], level-2: provider; level-3: ICU) to model the fixed effect of time, provider-level assessments (AITCS, HWEA,^{136,137} and ICU Care and Perceptions surveys), and their interactions on ICU-level adjusted performance rates. From the model, we can derive contrast estimates on the effect of change in

provider-level assessments on ICU-level bundle adoption. We will also extend the model to adjust for ICU-within-organization clustering.

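### Aim 1's model does not require an ICU term, so the overall effect of a patient characteristic that is unevenly spread over ICUs is tested with too small a standard error

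*Combined protocol and SAP*

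**What the plan says.** In Aim 1, Data analysis, the level-2 models fit the intercept, Month, Imp and Month×Imp coefficients "each as a linear function of fixed-effects of patient characteristics and patient-specific random effects". The stated purpose of the patient terms is to handle repeated days within a patient. If preliminary results allow, the model may be reduced to one with "fixed effect of patient gender, fixed effect of time, and patient-specific random effects". The same paragraph lists among the things the team can add to the model: "adjust for additional clustering (e.g., within-organization clustering". It also plans to "test the significance of hypothesized subgroup differences (e.g., older age, obese, and non-English speaking").

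ICU effects first appear as a planned term in Aim 2, Data Analysis, which examines variation across ICUs "by adding ICU-specific random effects to the model".

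Elsewhere the plan treats clustering by site as large:
- Aim 2, Sample Size/Power Analysis: "assuming an intraclass correlation of 0.3 for between-ICU variation based on our preliminary analysis".
- Aim 1, Power analysis: "a within-patient correlation of 0.5, and a within-hospital correlation of 0.6 in our simulation-based power calculation".
- Preliminary Data: "Bundle performance was highly variable among ICUs and across individual bundle elements".

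**The concern.** Patients in the same ICU share that ICU's level of bundle performance. If a characteristic is more common in some ICUs than in others, a model without an ICU term takes part of the difference between sites as an effect of the characteristic. It also computes the standard error as though some 15,000 patients were independent, when part of the information comes from only 68 units.

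Aim 1 is meant to identify patient-level barriers that later strategies will target. A test with a standard error half its true size can list a characteristic as a barrier when the signal is noise between sites. Aim 2 also keeps as case-mix covariates the characteristics found significant in Aim 1, but the harm there is small because ICU effects are added at that stage.

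There is a secondary point. Each patient contributes at most seven days, all in one of two periods separated by six months. Imp therefore never varies within a patient, and Month changes by at most one step. Patient-specific random effects on these terms have little or no within-patient information behind them.

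**Working it through.** **Inputs from the plan.** 15,226 patients in 68 ICUs, so 15,226/68 ≈ 224 per ICU; about 3.3 days per patient, maximum 7; between-ICU ICC 0.3; within-patient correlation 0.5; a characteristic with a 20:80 split; two-sided 0.05.

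**Assumed.** The share of a characteristic's variance that lies between ICUs (0% to 10%), and a lower ICC of 0.1 for comparison. The plan's within-hospital correlation of 0.6 was not used: it does not nest with a within-patient correlation of 0.5, because days of one patient also share a hospital.

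**The plan's own figure.** At ICC 0.3 and reliability 0.8, Spearman-Brown gives n = 0.8×0.7/(0.3×0.2) = 9.33, rounded up to 10, as stated in Aim 2. The plan gives no standard error or design effect for an Aim 1 overall effect.

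**Closed form.** True SD / reported SE ≈ √[1 + (m−1) × ICC × share], with m = 224 and ICC 0.3:
- 2%: √(1 + 223×0.3×0.02) = 1.53
- 5%: √(1 + 223×0.3×0.05) = 2.08
- 10%: √(1 + 223×0.3×0.10) = 2.77

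**Simulation of the written model.** There were 68 ICUs × 226 patients (5 a month for 6 months, 14 a month for 14 months) = 15,368 patients. The characteristic had no effect, and there was no level or slope change. Typical-patient probability was 0.30 at month 0. The logistic model had a patient random intercept only. Each scenario had 600 data sets.

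| Between-ICU share | 0% | 2% | 5% | 10% |
|---|---|---|---|---|
| Simplified model, ICC 0.3: ratio | 1.04 | 1.61 | 2.20 | 3.00 |
| type I error | 6% | 22% | 38% | 50% |
| Simplified model, ICC 0.1: ratio | 1.04 | 1.27 | 1.53 | 1.99 |
| type I error | 5% | 12% | 21% | 31% |
| Full model, implementation-period difference (contrast at month 7.5), ICC 0.3: ratio | 1.02 | 1.55 | 2.11 | 2.80 |
| type I error | 6% | 20% | 36% | 48% |

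A normal approximation agrees: at ratio 2.20, 2Φ(−1.96/2.20) ≈ 37%.

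A second simulation (224 patients per ICU, event probability about 0.4, 100 to 120 data sets per scenario) gave, at ICC 0.3, ratio 2.24 and 39% at a 5% share, and 2.87 and 48% at 10%. At ICC 0.1 and a 5% share it gave 1.50 and 18%. At an event probability of about 0.05, with ICC 0.3 and a 5% share, it gave 1.77 and 29%. At 0% share the ratio was 0.87, so there was no understatement. Monte Carlo error on these rates is up to about 9 points.

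**Tests that are not affected.** In the full model at ICC 0.3, type I error was 5–7% for level change, 5–6% for slope change, 5–6% for pre-period slope and 6–8% for pre-period level. An ICU effect that is constant over time largely cancels from a before/after contrast.

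**What produces such shares.** Share = w(1−w)(p1−p0)²/0.16, with overall prevalence 0.20. Aim 1, Setting and Sample puts 12% of patients in surgical/trauma ICUs, so w = 0.12.
- Twice as common there (0.357 against 0.179): 0.1056 × 0.1786²/0.16 = 2.1%. Simulated directly: ratio 1.53, type I error 21%.
- Three times as common (0.484 against 0.161): 0.1056 × 0.3226²/0.16 = 6.9%. Simulated directly: ratio 2.37, type I error 39%.

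**With an ICU random intercept (ICC 0.3).** At a 5% share: ratio 0.93, type I error 5% (100 data sets). In the three-times case: ratio 0.97, type I error 5% (80 data sets). In the second simulation, ICU intercepts gave 5% (40 data sets) and an ICU-clustered sandwich standard error on the patient-only model gave 4%.

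**Patient-level random slopes.** Within each period, the variance of a patient's linear predictor is a quadratic in Month, so it has three coefficients. Two periods give 6 estimable quantities, against 10 parameters in an unrestricted 4×4 covariance matrix. The intercept and Month variances and their covariance are estimable; the Imp and Month×Imp variances are not. With a diagonal matrix all four variances are identified (rank 4 of 4), but the Imp and Month×Imp variances only from how the spread between patients differs by month and period. The plan does not say which structure applies.

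**The case against.** The best defence is that an ICU term was intended. The authors often write that they can do something when they plan to do it, and multivariable adjustment sits in the same list of extensions. The Aim 1 power calculation includes a within-hospital correlation. Aim 2 says its strategy is that of Aim 1 and that clustering of patients within ICUs will again be adjusted for. This shows the wording is ambiguous about intent, but it does not put an ICU term in the Aim 1 model: the power text describes a simulation, Aim 1 offers clustering above the patient only as an extension, with organization as the example, and Aim 2 speaks of adding ICU effects.

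Several limits stand:
- The reach is narrow. The powered tests are sound, and the simplified model applies only if no level or slope change is found. Element E, the plan's own example, fits that better than complete or proportional performance, for which Preliminary Data reports a slope change and a level change respectively.
- The month-7.5 contrast is a choice made for this check, not an estimand the plan names.
- The between-ICU share is assumed. The documents support uneven spread for admitting diagnosis: it is a listed variable, and about 44% of patients were outside mixed medical/surgical units. They say nothing on the spread of age, obesity or language.
- A standard error half its true size needs a share of about 5% at ICC 0.3. The ratio is about 1.5 in the two-fold case, or at ICC 0.1 with a 5% share.
- The fix does not enlarge the reported standard error. The fault is that the patient-only estimator mixes in differences between sites and its standard error ignores them.

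The ICU-intercept fits above held ICU effects constant over time. In a linear analogue with ICU effects that change over time, the adjusted overall test stayed near nominal (4–6%).

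**Conclusion.** The concern holds and should be fixed; it is not fatal to the study. As written, the Aim 1 model and its simplified form leave ICU clustering unadjusted, while the plan's own figure for that clustering is an ICC of 0.3. For the overall effect of a characteristic with 2% to 10% of its variance between ICUs, the reported standard error is too small by a factor of about 1.6 to 3.0, and a nominal 5% test rejects a true null 22% to 50% of the time. At ICC 0.1 the range is 1.27 to 1.99 and 12% to 31%. With a 0% share there is no material problem. These sizes rest on the assumed shares, a 20% prevalence and an event probability of 0.30; at about 0.05 the inflation is smaller but still substantial. Confounding by site is possible and was not quantified. The patient-level random Imp and Month×Imp terms are not identified under an unrestricted covariance and are weakly supported under a diagonal one.

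**What to change.** In Aim 1, Data analysis, state that the primary model has days within patients within ICUs, with a patient random intercept and a mandatory ICU random intercept, and that this applies to the full segmented model, the simplified form and the Poisson version. Delete the patient-specific random Month, Imp and Month×Imp terms. ICU-level random level and slope changes, and within-ICU (ICU-mean-centred) effects, can be named as optional sensitivity analyses.

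The cost is one or two sentences, and Aim 2 already plans ICU random effects on the same data. The practical burden is more fitting and convergence checking across the complete, proportional and element outcomes. Reported precision for the overall effect did not suffer in simulation: the mean standard error was about 0.040 with the ICU intercept and 0.049 without it.
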